5.9 Rationale for this study

Different fertility drugs can cause nausea, diarrhea, constipation, abdominal pain,... It is unknown how many women suffer from these symptoms and how large the impact of these symptoms is during fertility treatment. The prevalence of IBS varies between 7,9 % to 49,3% in different studies, while the Rome Foundation Global study found a prevalence of 3,8%. (15, 28) The prevalence of IBS varies greatly between different subgroups. This study aims to give an indication of the prevalence and severity of gastrointestinal symptoms during fertility treatment. This knowledge can lead to better understanding and support during fertility treatment. Moreover, women undergoing fertility treatment will have an idea of what to expect when it comes to IBS-symptoms.

5.10 Rationale for study design

The role and significance of IBS symptoms in women who undergo fertility treatment has not yet been studied. Therefore, we designed this explorative study to get an overview of IBS symptoms during fertility treatment. There are many different subgroups of women undergoing a fertility treatment. This study chooses PCOS and social freezing. Women with PCOS are more at risk of developing gastrointestinal disturbances. (18) Elective oocyte cryopreservation is becoming more popular and this subgroup is a significant proportion of the women who come to the fertility clinic in UZ Brussels. Since it is predicted to become even more popular in the future, it would be helpful to explore the IBS symptoms during this treatment.

6 Study Objectives and Endpoints

6.1 Primary Objective

The primary objective of this study is to investigate whether fertility treatment is associated with changes in the **prevalence** and **severity** of Irritable Bowel Syndrome (IBS) symptoms. Specifically, the study aims to:

1. Assess whether the **proportion of participants meeting IBS diagnostic criteria** (based on ROME III and IV) differs **before and after fertility treatment**.
2. Evaluate whether there is a **statistically significant change in IBS symptom severity** as measured by the **IBS Symptom Severity Score (IBS-SSS)** before and after treatment.

6.1.1 Primary research hypotheses

H1.

The prevalence of participants meeting diagnostic criteria for Irritable Bowel Syndrome (IBS), as defined by the ROME III and ROME IV criteria, differs significantly before and after fertility treatment.

H2.

IBS symptom severity, as measured by the IBS Symptom Severity Score (IBS-SSS), changes significantly following fertility treatment compared with baseline.

6.2 Secondary Objectives

The secondary objective is to identify which **psychological and clinical factors** are associated with the presence or change in IBS symptoms in women undergoing fertility treatments, including those with **Polycystic Ovary Syndrome (PCOS)** and those undergoing **social oocyte freezing**.

The secondary objectives include:

- Changes in depression levels
- Changes in anxiety levels
- Differences in IBS symptoms based on the type of stimulation
- Differences in IBS symptoms based on the number of treatments received before this treatment
- Differences in IBS symptoms based on the duration of infertility
- Differences in IBS symptoms based on ethnicity
- Differences in IBS symptoms based on the type of PCOS
- Differences in IBS symptoms based on the hormonal profile during COS
- Differences in IBS symptoms based on the US reaction

6.2.1 Secondary research hypotheses

H3.

Changes in depressive symptom levels are significantly associated with changes in IBS symptom severity in women undergoing fertility treatment.

H4.

Changes in anxiety levels are significantly associated with changes in IBS symptom severity in women undergoing fertility treatment.

H5.

Changes in IBS symptoms differ significantly according to the type of ovarian stimulation used during fertility treatment.

H6.

Changes in IBS symptoms differ significantly based on the number of fertility treatments received prior to the current treatment.

H7.

Changes in IBS symptoms differ significantly according to the duration of infertility.

H8.

The prevalence and/or change in IBS symptoms differ significantly across ethnic groups.

H9.

Among women with Polycystic Ovary Syndrome (PCOS), changes in IBS symptoms differ significantly according to PCOS phenotype.

H10.

Changes in IBS symptoms are significantly associated with the hormonal profile during controlled ovarian stimulation (COS).

H11.

Changes in IBS symptoms differ significantly according to the ovarian response assessed by ultrasound during COS.

6.3 Endpoints

The IBS prevalence before and after the fertility treatment will be compared using the Rome Criteria for IBS. The severity of IBS symptoms before and after the fertility treatment will be compared using the IBS-SSS questionnaire. The difference in gastrointestinal symptoms before and after the fertility treatment will be compared using the GSRS questionnaire. The prevalence of anxiety levels before and after the fertility treatment will be compared using the GAD-7 questionnaire. The depression levels before and after the fertility treatment will be compared using the PHQ-9.

The PCOS and social freezing group will each be divided in different subgroups based on the type of stimulation. The IBS prevalence (with the Rome Criteria) and the IBS symptom severity (with the IBS-SSS) will be compared in these subgroups before and after the fertility treatment. The same will be done based on the duration of infertility, the ethnicity, the hormonal profile during COS and the US reaction. The PCOS group will be divided in different subgroups based on the type of PCOS. The IBS prevalence (with the Rome Criteria) and the IBS symptom severity (with the IBS-SSS) will be compared in these subgroups before and after the fertility treatment.

7 Study Design

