
Endpoints:
	
The primary endpoint is to explore whether there is a difference between the IBS prevalence before and after ovarian stimulation.
 
The score on the Rome Criteria for IBS before and after ovarian stimulation will be compared.
 
The severity of IBS symptoms before and after the fertility treatment will be compared using the IBS-SSS (IBS- Symptom Severity Scale) questionnaire.
 
The prevalence of gastrointestinal symptoms before and after the fertility treatment will be compared using the GSRS (Gastrointestinal symptom rating scale) questionnaire.
 
The prevalence of anxiety levels before and after the fertility treatment will be compared using the GAD-7 (Generalized Anxiety Disorder 7-item) questionnaire.
 
The depression levels before and after the fertility treatment will be compared using the PHQ-9 (Patient Health Questionnaire 9).
 
The PCOS and social freezing group will each be divided in different subgroups based on the type of stimulation.
 
The IBS prevalence (with the Rome Criteria) and the IBS symptom severity (with the IBS-SSS) will be compared in these subgroups before and after ovarian stimulation.
 
The same will be done based on the number of treatments that were received before this treatment, the duration of -infertility, the number of previous pregnancies, the number of children, the ethnicity, the hormonal profile during COS (continuous ovarian stimulation).
 
The PCOS group will be divided in different subgroups based on the type of PCOS. . The IBS prevalence (with the Rome Criteria) and the IBS symptom severity (with the IBS-SSS) will be compared in these subgroups before and after the fertility treatment.

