Participants will fill in the IBS-SSS and obtain a score between 0 and 500. The difference in score before and after the fertility treatment will be calculated. This score difference, which is a continuous outcome, will be used in a multiple linear regression model. This model estimates how several independent variables influence a single outcome. The regression analysis will show which independent variables (such as ethnicity, anxiety scores, duration of the desire to have children,...) have an influence on the score difference of IBS-SSS questionnaire. AIC will be used to evaluate the different possible models which will include different independent variables. The model with the lowest AIC will be used.

All analyses will be performed with SPSS.

11 Ethical Considerations

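### Sections 6.3 and 4 describe before/after comparisons within subgroups, but H5 and H7–H11 ask whether the change differs between them; section 10.5 covers this only in part

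*Protocol*

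**What the plan says.** **Hypotheses (section 6.2.1).** H5 reads "Changes in IBS symptoms differ significantly according to the type of ovarian stimulation used during fertility treatment". H7 reads "Changes in IBS symptoms differ significantly according to the duration of infertility". H9, for women with PCOS, says that "changes in IBS symptoms differ significantly according to PCOS phenotype". H11 makes the same kind of claim for ovarian response on ultrasound, and H10 states an association between change and hormonal profile. H8 is wider: "The prevalence and/or change in IBS symptoms differ significantly across ethnic groups".

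**Endpoints (section 6.3).** Each group is divided by type of stimulation, and Rome prevalence and IBS-SSS score "will be compared in these subgroups before and after the fertility treatment. The same will be done based on the duration of infertility, the ethnicity". This list goes on to hormonal profile and ultrasound reaction, and the same wording is used for PCOS type. The summary in section 4 has a parallel sentence, in which the outcomes "will be compared in these subgroups before and after ovarian stimulation". It covers most of these factors but not ultrasound reaction.

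**Analysis (section 10.5).** For IBS-SSS, each woman's before/after difference is the outcome of a multiple linear regression on independent variables "such as ethnicity, anxiety scores, duration of the desire to have children", followed by an ellipsis. For Rome status, a logistic model estimates the probability of meeting the criteria. Its list, also open, includes the anxiety and depression scores, ethnicity, how long the woman has wanted children, and follicle number. In both cases the model with the lowest AIC is the one used.

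**The concern.** A hypothesis that change differs by a factor has equal change at every level of that factor as its null. A before/after comparison inside one subgroup has no change in that subgroup as its null. The second does not answer the first. One subgroup significant and another not is no evidence that their changes differ, and all subgroups significant is no evidence that the changes are equal.

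If stimulation raises IBS-SSS by a similar amount in most women, separate tests in small subgroups will often give a mixture of significant and non-significant results, driven by subgroup size and chance. That could be read as support for H9 or H10. If the rise is large everywhere, every subgroup is significant and a real difference between phenotypes or hormone levels goes unseen. H5–H11 are worded in terms of significance, so tests are evidently intended even though the study is exploratory.

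**Working it through.** **1. Which stated analysis fits which hypothesis**

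| Hypothesis | Factor | Within-subgroup before/after wording | Named in the IBS-SSS change model (10.5) |
|---|---|---|---|
| H5 | stimulation type | 6.3 and 4 | no |
| H7 | duration of infertility | 6.3 and 4 | yes, taking time wanting children as its counterpart |
| H8 | ethnicity | 6.3 and 4 | yes |
| H9 | PCOS phenotype | 6.3 and 4 | no |
| H10 | hormonal profile | 6.3 and 4 | no |
| H11 | ultrasound response | 6.3 only | no; follicle number is named only in the logistic model |

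The logistic model describes IBS status. No time-by-factor term is stated, so it does not test whether the change in Rome status differs by factor.

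**2. Inputs for the size of the problem**

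The protocol gives 60 women per group (60 + 60 = 120) and states in section 4 that no power analysis was possible. There is therefore no power figure to reproduce. Assumed here: two-sided alpha 0.05, normal change scores, a mean change of d standard deviations, and the subgroup splits shown.

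**3. Power of one within-subgroup test**

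A paired t-test in n women has a noncentral t distribution with n − 1 degrees of freedom and noncentrality d√n. For n = 15 and d = 0.5, the noncentrality is 0.5 × √15 = 1.94 and the power is 0.438. At d = 0.3 the power is 0.192, and at d = 0.8 it is 0.821.

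**4. Identical change in all subgroups: chance of mixed verdicts**

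Four phenotypes of 15, with p the power of each test: 1 − p⁴ − (1 − p)⁴.

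- d = 0.3: 1 − 0.001 − 0.426 ≈ 0.57
- d = 0.5: 1 − 0.037 − 0.100 ≈ 0.86
- d = 0.8: 1 − 0.454 − 0.001 ≈ 0.54

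An uneven split of 30, 6, 9 and 15 gives 0.59, 0.90 and 0.84. With no change in anyone, at least one of four subgroups is significant with probability 1 − 0.95⁴ = 0.185.

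Two halves of 30: 2p(1 − p).

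| d | p | mixed verdicts |
|---|---|---|
| 0.2 | 0.185 | 0.30 |
| 0.3 | 0.355 | 0.46 |
| 0.4 | 0.563 | 0.49 |
| 0.5 | 0.754 | 0.37 |
| 0.8 | 0.988 | 0.02 |

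A direct test of equal mean change has a 5% error rate in all these cases by construction.

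**5. A real difference missed**

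Take d = 0.5 in one half and 1.0 in the other, 30 women each. The within-subgroup powers are 0.754 and about 1.0, so both are significant in about 75% of studies and the verdicts differ in about 25%. A direct two-sample test on change has noncentrality 0.5/√(2/30) = 1.94 on 58 degrees of freedom, and power 48%. With 60 women in each subgroup the figures are 3% differing verdicts against 78% power.

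**6. How much Rome status could support**

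Section 9.3.1 quotes overall prevalences of 3.8% (Rome IV) and 10.1% (Rome III). In 60 women these give 60 × 0.038 ≈ 2 and 60 × 0.101 ≈ 6 cases. Doubled for PCOS, following the twofold risk in section 5.6, they give about 5 and 12. Section 5.9 also cites prevalences from 7.9% to 49.3%, so the number could be higher. At the lower figures, four phenotypes could not carry a formal interaction test.

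**The case against.** The strongest reply is that section 10.5 already contains the right analysis. It regresses each woman's IBS-SSS difference on covariates, restates the aim of finding clinical factors linked to presence or change of symptoms, and gives open lists. Naming every covariate is commonly left to a statistical analysis plan, which was not at hand. Section 6.3 is an endpoints section: it names no test, and its wording could also mean that subgroups are compared with each other at both times.

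Much of this stands. A reader might infer that the protocol has no test of differential change at all. It does have one for IBS-SSS, and for H7 and H8 the factor or its close counterpart is named. A reader might also infer that differences will be declared whenever one subgroup is significant and another is not; no such rule is written. Nor is it stated that hormone levels or follicle counts will be split at the median. Sections 6.3 and 4 speak of subgroups without cut-points, and section 10.5 enters duration and, in the logistic model, follicle number as regression variables. A power loss computed for a median split would therefore rest on a split that the protocol does not specify.

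The conflict remains. For the same hypotheses, sections 6.3 and 4 point on their natural reading to a comparison with the wrong null, and section 10.5 points to another analysis. The short list in 10.5 is not an error in itself. It matters because, for stimulation type, phenotype, hormonal profile and ultrasound response, only the within-subgroup wording expressly links the factor to change. Open lists also do not prevent AIC selection from removing a factor under test.

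**Conclusion.** The point holds as an inconsistency within the protocol that should be corrected. It is clearest for H5, H9, H10 and H11, and for any claim about change in Rome status. It is weaker for H7 and the change part of H8, where section 10.5 already offers a suitable IBS-SSS test, subject to AIC selection. The prevalence part of H8 can be addressed by the logistic model, which names ethnicity.

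The error rates apply only if within-subgroup tests are used to judge these hypotheses. They also depend on the assumed alpha, effect size and split: mixed verdicts under identical change range from 2% (two halves of 30 at 0.8 SD) to about 90% (four uneven phenotypes at 0.5 SD). The exploratory design lowers the stakes but does not remove the mismatch.

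**What to change.** - In sections 6.3 and 4, state that H5, H7, the change part of H8, and H9–H11 are each tested by that factor's term in the section 10.5 model of IBS-SSS change. Phenotype is one joint test over the four types, in the PCOS group only.
- In section 10.5, name these factors and state that the term under test stays in the model whatever the AIC. AIC may still choose among the other covariates.
- State that before/after results within subgroups, for IBS-SSS and for Rome status, are descriptive and that no claim of a subgroup difference is drawn from them.
- Enter hormone levels and follicle number as continuous variables, and duration of infertility likewise where it is defined. It may not be defined for many social freezing participants, since section 5.3 gives lack of a partner as their main reason.
- For H5, say what the levels of stimulation type are, because sections 4 and 8.1 put both groups on the same PPOS approach.

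The cost is wording in three places, with no new data. There will be fewer nominally significant subgroup statements. A linear form is assumed for the continuous factors, which a plot can check.

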Study population:	Nulliparous women with a diagnosis of PCOS who are eligible for IVF (in vitro fertilization) treatment with freeze-only strategy (i.e. deferred embryo transfer). Nulliparous women who embark on elective oocyte

	
cryopreservation. Both groups will receive PPOS (progestin-primed ovarian stimulation).

In- and exclusion criteria:	
Inclusion criteria PCOS group :
 
 - Diagnosis of PCOS according to the 2004 Rotterdam criteria - Initiating their first cycle of IVF treatment (PPOS and freeze only protocol) - Nulliparous - ≥ 18 years - Willing to participate in the study - Understanding Dutch, French or English 
Exclusion criteria PCOS group :
 
 - Known inflammatory bowel disorder - Known major intestinal bowel disorder - Known systemic or auto-immune disorder with implication for the GI system - History of abdominal surgery (appendectomy and cholecystectomy allowed if >6 months earlier) - History of gastro-enteritis in the past 6 weeks - Previous IVF treatment cycles 
Inclusion criteria social freezing group:
 
 - Initiating their first ovarian stimulation protocol for elective oocyte cryopreservation (PPOS and freeze only protocol) - Nulliparous - ≥ 18 years - Willing to participate in the study - Understanding Dutch, French or English 
Exclusion criteria social freezing group:
 
 - Diagnosis of PCOS - Known inflammatory bowel disorder - Known major intestinal bowel disorder - Known systemic or auto-immune disorder with implication for the GI system - History of abdominal surgery (appendectomy and cholecystectomy allowed if >6 months earlier) - History of gastro-enteritis in the past 6 weeks
Factors of interest / Data to be collected:	
IBS diagnosis and symptom severity Gastrointestinal symptom severity Depression levels Anxiety levels
 
Factors to be collected before ovarian stimulation:
 
 • Demographics (length, weight) • The duration of infertility • Obstetrical history: GPA (Gravida, Para and abortus) • The ethnicity • For the study group: the type of PCOS 
Factors to be collected after oocyte pick-up:
 
 • The hormonal profile at start and end of ovarian stimulation • The number of follicles on the last ultrasound before pickup • The number of COC (Cumulus-oocyte complex) collected during pick-up

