10.5 Statistical Considerations and Data Analysis

The primary objective of this study is to investigate whether fertility treatment is associated with changes in the **prevalence** and **severity** of Irritable Bowel Syndrome (IBS) symptoms. Specifically, the study aims to:

3. Assess whether the **proportion of participants meeting IBS diagnostic criteria** (based on ROME III and IV) differs **before and after fertility treatment**.
4. Evaluate whether there is a **statistically significant change in IBS symptom severity** as measured by the **IBS Symptom Severity Score (IBS-SSS)** before and after treatment.
5. Identify which **psychological and clinical factors** are associated with the presence or change in IBS symptoms in women undergoing fertility treatments, including those with **Polycystic Ovary Syndrome (PCOS)** and those undergoing **social oocyte freezing**.

Participants will either meet the criteria for IBS or not meet the criteria for IBS (based on the ROME III and IV criteria). This will correlate to a binary outcome: yes (1) or no (0) answer. This answer will be defined before and after the fertility treatment. A logistic regression model will be used to determine the chance of P(1) which is the chance of meeting the IBS criteria (yes answer). This regression model will be used for the PCOS group and the social freezing group. This model estimates the probability of an event occurring (meeting the IBS criteria) based on a given set of independent variables. The independent variables include GAD-7 score, PHQ-9 score, ethnicity, duration of the desire to have children, the number of follicles found on the US,...

These independent variables will be evaluated with the AIC (Akaike information criterion). AIC is used to compare different possible regression models and define which model is the best fit for the given data. If the AIC is lower, the data is a better fit. The regression model will be made with different independent variables and each time the AIC will be calculated. The model with the lowest AIC will be the final model.

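### Section 6.3 divides women into subgroups by duration of infertility, hormonal profile and ultrasound response, which are numeric factors; section 10.5 puts duration and follicle number into regressions with no grouping stated, and the two are not reconciled

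*Protocol*

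**What the plan says.** Protocol section 6.3 first sets the rule: "The PCOS and social freezing group will each be divided in different subgroups based on the type of stimulation". IBS prevalence by the Rome criteria and IBS-SSS severity are then compared in those subgroups before and after treatment. The rule is extended: "The same will be done based on the duration of infertility, the ethnicity, the hormonal profile during COS and the US reaction".

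The Endpoints row of section 4 has a similar sentence, beginning "The same will be done based on the number of treatments that were received before this treatment, the duration of -infertility". Its list goes on to include the hormonal profile but not the ultrasound response.

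The data-collection row of section 4 describes the factors as "The duration of infertility", "The hormonal profile at start and end of ovarian stimulation" and "The number of follicles on the last ultrasound before pickup". The follicle count is the only ultrasound measurement listed, so it is the natural reading of the ultrasound response in section 6.3 and H11.

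Section 10.5 describes a different analysis. For Rome IBS status there is a logistic regression: "The independent variables include GAD-7 score, PHQ-9 score, ethnicity, duration of the desire to have children, the number of follicles found on the US". For IBS-SSS change there is a multiple linear regression, and its examples again include the duration variable. Neither description mentions grouping, and neither names the hormonal profile, although both lists are left open-ended.

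The protocol gives no cut-point, number of categories or rule for forming groups.

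**The concern.** Ethnicity, type of stimulation and PCOS phenotype are categories, so subgroups suit them. A length of time, a hormone level and a follicle count are quantities. Grouping them treats all women within a group as alike, and so discards information in a study of 60 women per group with no prior power calculation. It also opens a choice of where to cut, and each cut tried is a further test of the same hypothesis.

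The second difficulty is that sections 6.3 and 10.5 give different analyses of the same question. H7 (duration) and H11 (ultrasound response) can be tested by comparing subgroups or by a regression coefficient. The two can disagree, and the protocol does not say which decides. For H10 (hormonal profile) the only route named is the subgroup comparison. All three hypotheses are worded in terms of statistical significance, so both lost power and extra false positives bear on what will be claimed.

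**Working it through.** **Inputs.** From the protocol: 60 women per group, 60 + 60 = 120 in total (section 4). The protocol gives no figure for power, effect size or information loss, so there is none to reproduce. Assumed here: two-sided 5% tests, a linear effect, no dropout, and a normal factor unless stated otherwise.

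**Step 1: information kept after grouping.** For a standard normal factor cut into groups k with probability P_k and limits a and b, the group mean is m_k = (φ(a) − φ(b)) / P_k. The share of information kept is Σ P_k m_k².

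- Median split: m = ±0.399 / 0.5 = ±0.798. Kept: 2 × 0.5 × 0.798² = 0.637 (that is, 2/π). Lost: 36%.
- Tertiles: outer means ±1.091, middle mean 0. Kept: 2 × (1/3) × 1.091² = 0.793. Lost: 21%.
- Quartiles: kept 0.861, lost 14%. Quintiles: kept 0.897, lost 10%.
- Uneven two-group cuts: 30/70 loses 42%, 25/75 loses 46%, 20/80 loses 51%, 10/90 loses 66%.
- Median split of other shapes: uniform loses 25%, lognormal (log-SD 0.5) 48%, exponential 52%.

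These figures score each group by its mean. An unordered comparison of three or more groups also spends degrees of freedom, so its power is lower than they suggest.

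**Step 2: what a median split costs in power at n = 60.** By Fisher's z, the correlation that gives 80% power is r = tanh((1.960 + 0.842) / √57) = 0.355. A median split shrinks it to 0.355 × √0.637 = 0.283. Power is then Φ(atanh(0.283) × √57 − 1.960) = 0.59. This is like using 60 × 0.637 ≈ 38 of the 60 women. With both groups pooled (n = 120, r = 0.253) power falls from 80% to 60%.

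**Step 3: false positives if the cut is chosen on the data.** Simulation with 20,000 data sets, no true effect, and two-sample t-tests at 5%, keeping the smallest p-value over the cuts allowed:

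| Cut chosen from | n = 60 | n = 120 |
|---|---|---|
| One cut fixed in advance at the median | about 5% | about 5% |
| Two tertile cuts and the median | 11–12% | 11–12% |
| Anywhere in the middle 50% of the data | 25.4% | 26.9% |
| Anywhere in the middle 60% | 28.7% | 30.5% |
| Anywhere in the middle 80% | 38.6% | 40.7% |

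**Step 4: the sections side by side.**

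| Factor | Section 4, Endpoints | Section 6.3 | Section 10.5 |
|---|---|---|---|
| Duration (H7) | subgroups | subgroups | named in both regressions, no grouping stated |
| Hormonal profile (H10) | subgroups | subgroups | not named |
| Ultrasound response (H11) | not listed | subgroups | follicle number named in the logistic regression, no grouping stated |

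**The case against.** The strongest reply is that cut-points for secondary, exploratory comparisons normally belong in a SAP, which is not at hand, and that section 10.5 already contains most of the remedy. The first part stands as far as it goes: missing cut-points alone would not be a finding. But forming subgroups is a choice that the protocol itself states, and a SAP that follows it inherits both that choice and the conflict with section 10.5. The second part stands for duration and follicle number only. The hormonal profile could enter through the open-ended lists, but it is not named.

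Three stronger readings are tempting and are not supported.

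- A reader might infer that the plan throws away about a third of the information. That figure belongs to a median split of a roughly normal factor. The protocol states neither the number of groups nor where they divide, and the loss does not carry over to the section 10.5 regressions.
- A reader might infer that the investigators will pick the most favourable cut, with a false-positive rate of 25% to 39%. Nothing in the protocol says so. With one cut fixed in advance, each test stays near 5%.
- A reader might infer that section 4 also plans subgroups by ultrasound response. It does not; only section 6.3 does.

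It is also fair to say that the study calls itself explorative. That lowers the stakes, but H7, H10 and H11 are still phrased as significance claims.

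**Conclusion.** The point holds in this form: sections 4 and 6.3 commit to a weaker method for numeric factors, and section 6.3 is not reconciled with section 10.5. The follicle count is explicitly numeric. For duration and hormone levels this is a plain inference, since the protocol gives no units and names no hormones.

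The size depends on a grouping that the protocol does not specify: about 10% of the information with quintiles, 21% with tertiles, 36% with a median split, and over 50% with uneven cuts or a strongly skewed factor. The quintile, tertile and median-split figures assume a normal factor, and all assume a linear effect. The false-positive range of 25% to 39% at n = 60 is conditional on a cut chosen freely on the data, which the protocol does not state but does not prevent. The point concerns secondary hypotheses and does not touch the two primary comparisons.

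**What to change.** Align sections 4 and 6.3 with section 10.5:

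- Analyse all three factors as continuous values, log-transformed if skewed. Use duration of infertility in the women to whom it applies; section 5.3 gives lack of a partner as the main reason for social freezing, so it may not apply to many in that group. Use hormone levels for a named hormone and time point chosen before the data are seen. Use the follicle count as it stands.
- Use one defined duration variable throughout. Sections 4 and 6.3 refer to infertility, while section 10.5 lists "ethnicity, duration of the desire to have children, the number of follicles found on the US".
- Fit a linear model for IBS-SSS change and the matching logistic model for Rome IBS status, so that the prevalence comparison in section 6.3 is kept.
- Name the slope on IBS-SSS change as the deciding test of H7, H10 and H11. Report it whether or not the AIC search in section 10.5 retains the factor, since otherwise a dropped factor has no test.
- Keep subgroups for the true categories: type of stimulation (H5), ethnicity (H8) and PCOS phenotype (H9).
- If grouped tables are wanted for the numeric factors, fix the groups in advance and give no p-values.

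The cost is wording, plus the choice of a hormone and time point; the data are already to be collected. The downside is that a linear slope can miss a threshold effect, which can be checked with a plot of IBS-SSS change against each factor.
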